6.6 Interim Analysis

No interim analysis will be performed for this study.

The final analysis of the primary and secondary immunogenicity endpoints will be conducted on cleaned and locked data once all subjects have completed all immunogenicity assessments (end of treatment period, i.e. up to 28 days following the last vaccination dose). At this time, the analysis of all solicited adverse events and of unsolicited adverse events reported during the treatment period will also be conducted. These results will be used to prepare a Clinical Study Report (CSR) with treatment period data. No individual unblinded listings will be generated at this stage.

This analysis constitutes the final analyses of the primary and secondary immunogenicity endpoints and therefore preserves the integrity of the clinical study results.

7. Changes in Planned Analysis

“Evaluable Set – Immunogenicity” population as been renamed as “Full Analysis Set – Immunogenicity”.

Any deviations from the original statistical plan will be described and justified in the final CSR.

8. Data Issues

Not applicable.

9. References

- 1 Clinical Study Protocol V130_10 Protocol_v4_09DEC2019.pdf
- 2 ICH. *Statistical Principles for Clinical Trials*, Guideline E9, 1998. Available at <http://www.emea.eu.int/pdfs/human/ich/036396en.pdf>
- 3 World Health Organization, WHO Technical Report, Series No. 924. 2004, Annex 1: *Guidelines on Clinical Evaluation of Vaccines: Regulatory Expectations*
- 4 FDA CBER Guidance for Industry, May 2007, *Clinical Data Needed to Support the Licensure of Seasonal Inactivated Influenza Vaccines*
- 5 ICH guideline (Guidance for Industry, Clinical Safety Data Management: Definitions and Standards for Expedited Reporting – ICH-E2A), 27 October, 1994

Appendix A: Schedule of Assessments

The schedule chart is the master representation of the clinical trial. In case of (apparent) inconsistencies in the clinical trial protocol the information provided here is the binding one.

Time and Events Table – Previously Vaccinated Subjects

	Treatment Period			Follow-up Period	
	Clinic Visit	Reminder Phone Call	Clinic Visit	Safety Phone Call	Safety Phone Call
Visit Number	V1		V2	V3	V4
Study Day		V1 + 2	V1 + 28	V1 + 90	V1 + 180
Study Day Window	n/a	-1/+1	0 to +7	0 to + 7	0 to + 14
Informed Consent *	X ^b				
Medical History	X ^b				
Physical Examination and Clinical signs	X ^{b,c}		X		
Exclusion/Inclusion Criteria	X ^b				
Randomization	X ^b				
Vaccination	X				
30 Minutes Post Vaccination Assessment	X				
Subject Diary Card Dispensed with Training	X				
Subject Diary Card Reminder Call		X			
Subject Diary Card Reviewed and Collected			X		
Assess all AEs	X		X		
Assess SAEs, NOCDs, AEs leading to withdrawal	X		X	X	X
Assess Relevant Medications/Vaccinations	X		X	X	X
Blood Draw	X ^{b,d}		X ^d		

Abbreviations: AE = adverse event; n/a = not applicable; NOCD = new onset of chronic disease; SAE = serious adverse event; V = visit.
^a Confirm consent form(s) signed prior to any procedures. The informed consent process may be conducted earlier, but within 10 days prior to Day 1.
^b Procedures to be performed prior to vaccination.
^c Includes measurement of height and weight.
^d A blood sample will be drawn prevaccination (Day 1) and postvaccination (Day 29) for immunogenicity evaluation or for assessing cell-mediated immunity response.

Statistical Analysis Plan

Sponsor Name: Seqirus
 Sponsor Protocol ID: V130_10

Time and Events Table – Not Previously Vaccinated Subjects

	Treatment Period					Follow-up Period	
	Clinic Visit	Reminder Phone Call	Clinic Visit	Reminder Phone Call	Clinic Visit	Safety Phone Call	Safety Phone Call
Visit Number	V1		V2		V3	V4	V5
Study Day		V1 + 2	V1 + 28	V2 + 2	V2 + 28	V2 + 90	V2 + 180
Study Day Window	n/a	-1/+1	0 to+7	-1/+1	0 to +7	0 to +7	0 to +14
Informed Consent ^a	X ^b						
Medical History	X ^b						
Physical Examination and Clinical signs	X ^{b, c}		X		X		
Exclusion/Inclusion Criteria	X ^b		X ^{b, d}				
Randomization	X ^b						
Vaccination	X		X				
30 Minutes Post Vaccination Assessment	X		X				
Subject Diary Card Dispensed with Training	X		X				
Subject Diary Card Reminder Call		X		X			
Subject Diary Card Reviewed and Collected			X		X		
Assess all AEs	X		X		X		
Assess SAEs, NOCDs, AEs leading to withdrawal	X		X		X	X	X
Assess Relevant Medications/Vaccinations	X		X		X	X	X
Blood Draw	X ^{b, e}				X ^e		
Abbreviations: AE = adverse event; n/a = not applicable; NOCD = new onset of chronic disease; SAE = serious adverse event; V = visit. ^a Confirm consent form(s) signed prior to any procedures. The informed consent process may be conducted earlier, but within 10 days prior to Day 1. ^b Procedures to be performed prior to vaccination. ^c Includes measurement of height and weight. ^d Eligibility for subsequent vaccination (see 5.2.2). ^e A blood sample will be drawn prevaccination (Day 1) and postvaccination (Day 57) for immunogenicity evaluation or for assessing cell-mediated immunity response.							

Appendix B: Sample SAS® code for analyses

- **Tables that need descriptive statistics – continuous variables:**

```
[REDACTED]
```

- **Tables that need frequency counts:**

```
[REDACTED]
```

- **Tables that need exact (Clopper-Pearson)95% CIs between groups for proportions:**

```
[REDACTED]
```

Notes: 1 Estimates are computed for 2x2 tables only
2 This code also gives exact 95% CIs within group for binomial proportions

- **Tables that need Miettinen-Nurminen 95% CIs for proportion differences:**

```
[REDACTED]
```

- **Tables that need 95% CIs within group for binomial proportions:**

```
[REDACTED]
```

- **Code to create 95% CIs within group for continuous variables:**

```
[REDACTED]
```

- **General linear model (adjusted analysis for GMT ratio):**

```
[REDACTED]
```

Statistical Analysis Plan

Sponsor Name: Seqirus
Sponsor Protocol ID: V130_10

[REDACTED]

[REDACTED]

- **The geometric mean is the antilog of the arithmetic mean of the logs:**

[REDACTED]

Appendix C: Sensitivity Analyses for Handling of Missing Immunogenicity Data

To verify the robustness of the primary analysis results, an exploratory analysis will be performed, in which missing titers were imputed using multiple imputation. The evaluation of the robustness of the primary analysis results will be based on a pattern mixture model and a 'tipping analyses' approach using multiple imputation methods.

This sensitivity analysis will be based on the per-protocol analysis set and will serve to evaluate the robustness of the non-inferiority conclusions.

An overview of the methods of imputation for each of the estimands GMT and binary endpoint SCR are specified below. The results based on the imputed data and the results of the same analyses performed on the original, non-imputed data using multiple imputation procedures will be compared.

GMT Missing Data Evaluation

The ANCOVA are valid when the missing data are Missing at Random (MAR). There is no reason to question MAR assumption for baseline data, but MAR cannot be established for follow-up observations.

The approach to evaluating the impact of missing serology data is based on finding the existence of evidence against the assertion that the observed results are not explained by the existence of missing data. The framework to be used for finding such evidence is the based on the Pattern Mixture Multiple Imputation (PMMI) (Little 2013). PMMI will provide assessments of missing data sensitivity.

For this exploratory analysis imputation sampling will be done using the non-missing data in pattern subsets because the expected data do not follow a defined statistical distribution. Usually PMMI implementations use Markov Chain Monte Carlo (MCMC) imputation sampling based on known statistical distributions, for example a multivariate normal. The disadvantage of sampling from non-missing data is the loss of a specified correlation structure possible when using a defined statistical distribution. The use of smaller pattern groups, however, do provide some preservation of observed within patient correlation.

A SAS macro has been created for doing PMMI as described. This macro allows sampling from subsets (patterns) defined for a list of categorical variables. It computes the mean results over multiple imputations using the previously discussed models. The missing data in either arm can be sampled from the non-missing data from either arm to impute data in each arm. The missing baseline data can also be imputed according to the patterns specified. The primary focus will be to estimate the results when missing data in both the control and experimental arms are imputed from sampling from the non-missing data in the control arm, and when missing data in both the control and experimental arms are imputed from sampling from the non-missing data in the experimental arm, The latter analysis provides an additional

[figure not shown]
Statistical Analysis Plan

Sponsor Name: Seqirus
Sponsor Protocol ID: V130_10

sensitivity assessment appropriate for non-inferiority evaluations. The macro allows for covariates other than baseline (as used in the ANCOVA model specification for the primary analysis).

Seroconversion Binary Outcome Analyses

Analysis of the seroconversion binary outcome, SCR, is also expected to have missing data. An excellent method of assessing the impact of missing outcomes for a binary outcome is to make a tipping point graph (Yan 2009). A tipping point graph has as its two axes corresponding to the two arms. Each axis ranges from zero to the number of missing values in the corresponding arm. For each possible combination of possible assignments of missing from non-success to success the statistical test is recomputed. In this evaluation we apply sensitivity analysis based upon multiple imputations under the by searching for a tipping point by using "shift" approaches until the inferences change from significance to non-significance, or vice versa. Those analyses meeting statistical criterion are graphed as a point with a colored symbol showing success and the analyses failing statistical criterion are graphed as a point using a symbol of a contrasting color. In general, this graph will then show two regions defined by the colors assigned. The location of the analysis using the default assignment for missing outcome (usually missing is regarded as a non-success) will then be in one of these regions, and the distance this point is from the other region can be assessed as a sensitivity analysis. The statistical test can be based on the usual two group assessment (asymptotic or exact) or with covariates using logistic regression. The following is an example of a tipping point graph.

Statistical Analysis Plan

Sponsor Name: Seqirus
Sponsor Protocol ID: V130_10

REFERENCES

Yan 2009] Yan X, Lee S, Li N. Missing data handling methods in medical device clinical trials, *J Biopharm Stat.* 2009 19(6):1085-98.

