4.4 Full Analysis Set – Immunogenicity

The FAS for immunogenicity analyses will comprise all subjects in the FAS who:

- receive vaccine on Day 1
- provide serology specimens which yield valid serology assay results from both Day 1 and Day 29 (Previously vaccinated subjects) or Day 1 and Day 57 (Not previously vaccinated subjects)

The FAS will be used to produce summaries and listings of subject characteristics.

In case of vaccination error, subjects in the FAS Immunogenicity will be analyzed “as randomized” (i.e., according to the vaccine a subject was designated to receive, which may be different from the vaccine the subject actually received).

If a subject is unblinded during the study, he/she will be included in the FAS Immunogenicity.

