4.5 Per Protocol Set (PPS)

The PPS will comprise all subjects in the FAS Immunogenicity who do not have any protocol deviations that are medically assessed as potentially impacting on immunogenicity results.

The PPS will be the primary set of interest for the primary/secondary immunogenicity analysis and a supporting analysis will be performed using the FAS Immunogenicity. Membership of the PPS will be determined prior to unblinding the study.

Duplicate tables of primary and secondary immunogenicity analyses may also be produced based on the FAS Immunogenicity population if there is >5% difference in the total number of subjects between the Per-Protocol Population and the FAS Immunogenicity Population. The decision to produce tables based on the FAS Immunogenicity Population will be made by Seqirus after population sets are finalized and prior to unblinding.

Examples for subjects excluded due to other reasons than protocol deviations are subjects who withdrew informed consent.

In case of misrandomization with regard to treatment arm, the subject is excluded from the PPS.

If a subject is unblinded during the study, except for SUSAR, he/she will be excluded from the PPS.

If the serum sample was collected outside the time window of 21 days, the subject did not comply with the blood draw schedule and will be excluded from the PPS population. Hence, subjects will be excluded from PPS if blood draws >21 days after any vaccination.

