4.5.1 Important Protocol Deviations Leading to Exclusion from the PPS Analysis

A protocol deviation (PD) is any change, divergence, or departure from the study design or procedures of a study protocol. A protocol deviation may be a reason to remove data from an analysis set at the time of analysis. PDs can be either observable or programmable. Programmable PDs are those PDs that can be programmed from the data recorded in the clinical database. Observable PDs are PDs identified by CRAs or other team members.

PDs will be classified as major and minor using a prespecified list of types of deviations. Major PDs are defined in accordance with ICH E3 as important PDs related to study inclusion or exclusion criteria, conduct of the trial, subject management or subject assessment resulting in the potential to jeopardize the safety or rights of the trial subjects or the scientific value of the trial.

All PDs will be evaluated before unblinding and most will be classified into the following categories:

- Subject randomized and did not satisfy entry criteria
- Subject received the wrong treatment or incorrect dose
- Subject took an excluded concomitant medication
- Key study procedures missed or performed out of window, such as, for immunogenicity if the serum sample was collected outside the time window of 21 days the subject did not comply with the blood draw schedule and will be excluded from the PPS population. Hence, subjects will be excluded from PPS if blood draws >21 days after any vaccination.

The impact of major PDs on the efficacy, immunogenicity and/or safety results will be investigated by assessing the robustness of the study results.

Major PDs will lead to exclusion of the subject or part of the subject's data from at least one analysis set.

The number of subjects in any and by PD category will be summarized by treatment group, center and overall. Individual subject listings will be provided in an appendix, sorted by subject and by PD category.

Prior to unblinding the analysis, designated Seqirus staff will develop a memo that describes the PDs that led to exclusions from analysis sets. This memo will be signed off by at least the Biostatistician and the Clinical Scientist and will be included in the trial master file (Exclusion Memo).

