6.5.1.3 Statistical Methods

All statistical analyses for HAI (or MN) titers will be performed on the logarithmically transformed (base 10) values. Individual HAI titers below the detection limit (<10) will be set to half of that limit (5). Individual MN titers below the LLOQ, will be set to half of that limit ($1/2 * \text{LLOQ}$).

Co-primary immunogenicity endpoints of GMT and SCR for each virus strain contained in the vaccine will be assessed in subjects 6 Months through 47 Months of Age overall.

Statistical Analysis Plan

Sponsor Name: Seqirus
Sponsor Protocol ID: V130_10

Primary analysis will be performed in subjects 6 Months through 47 Months of Age for the Per-Protocol Set. The difference in SCRs will be presented with exact 95% CIs. Each of the four strains will be analyzed separately.

For immunogenicity data, the immunogenicity analysis will comprise a complete case analysis only, without introducing any bias. Imputation methods will not be used.

To determine the GMT ratio (adjusted analysis) a general linear model (GLM) will be fitted on log transformed (base ten) post-vaccination HAI (or MN) titer as the outcome variable and terms for covariates: vaccine treatment, pre-vaccination HAI (or MN) titer, age stratum, gender, vaccination history, age-by-vaccine interaction and study site. Potential covariate interaction effects will also be examined in the fit of the GLM. From the model, an adjusted difference in least square means (on the log scale) will be produced with 95% confidence limits. The estimated difference and the confidence limits will be back transformed to obtain an *adjusted GMT ratio* with 95% confidence limits. Each of the four strains will be analyzed separately. The adjusted GMT ratio will be the result for which the non-inferiority assessment of the HAI (or MN) GMT co-primary endpoint will be based on.

The statistical models might be reduced in case they fail to converge.

The complete set of covariates that will be used in the model to calculate the adjusted GMT ratio will include treatment group (2 treatments), pre-vaccination GMT titer (value), age strata (2 categories, 6 through 23 months or 24 through 47 months), gender (male or female), influenza vaccination received prior year (Yes or No), and investigator site (site identifier).

The GLM specification is:

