Adjusted Analysis GMT Model: Log-transformed Post-vaccination HAI (or MN) Titer = Vaccine + Age Strata + Gender + Vaccination History [y/n] + Log-transformed Pre-vaccination HAI (or MN) Titer + Site + Age Strata*Vaccine.

For any strain, the interaction term Age Strata*Vaccine will be removed from the fit of the model if it is assessed to be not significant. For all immunogenicity subgroup analysis, the interaction term will be removed in the fit of the model.

The measure of the unadjusted GMT ratio based on post-vaccination GMTs only will also be presented.

Binary data (i.e., percentages of subjects with seroconversion and with titer $\geq 1:40$) will be summarized for each group using unadjusted estimates and will be reported together with two-sided exact 95% CIs. No multiplicity adjustment to the CI levels will be implemented.

If all 8 co-primary endpoints result in a conclusion of non-inferiority, then overall non-inferiority of Seqirus QIVc compared to the US-licensed comparator QIV will be concluded.

Handling of Missing Values for Immunogenicity Data

For immunogenicity data, it may be reasonable to consider missing immunogenicity values as missing completely at random (MCAR), i.e., not informative. Therefore, the immunogenicity and key secondary analyses will comprise a complete case analysis only, without introducing any bias. Imputation methods will not be used.

Sensitivity Analyses for Handling of Missing Immunogenicity Data

To verify the robustness of the primary analysis results, an exploratory analysis may be performed, in which missing titers were imputed using *multiple imputation*. The evaluation of the robustness of the primary analysis results will be based on a pattern mixture model and a 'tipping analyses' approach using multiple imputation methods.

This sensitivity analysis, if conducted, will be based on the per-protocol analysis set and will serve to evaluate the robustness of the non-inferiority conclusions. Appendix C specifies the details of the exploratory sensitivity analysis.

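### The missing-titer sensitivity analysis is run in the Per Protocol Set, whose entry rule has already removed children without valid serology at both visits, so missing samples are never imputed

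*SAP*

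**What the plan says.** SAP 6.5.1.3 makes the primary analysis a complete-case analysis in the PPS, on the view that missing titers are missing completely at random. It then allows an exploratory check by multiple imputation, pattern mixture and tipping point: "This sensitivity analysis, if conducted, will be based on the per-protocol analysis set". Appendix C gives the details and names the same set: "This sensitivity analysis will be based on the per-protocol analysis set and will serve to evaluate the robustness of the non-inferiority conclusions".

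The set definitions are in SAP section 4. Section 4.5 says: "The PPS will comprise all subjects in the FAS Immunogenicity who do not have any protocol deviations". Section 4.4 requires children in the FAS Immunogenicity to "provide serology specimens which yield valid serology assay results from both Day 1 and Day 29" (Day 57 for those not previously vaccinated). Protocol 8.3.4 sets the same condition for the Evaluable Set, which SAP section 7 says was renamed.

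Appendix C nevertheless expects missing values in its population. On baseline titers it says: "The missing baseline data can also be imputed according to the patterns specified". For seroconversion it describes a tipping-point grid with one axis per arm, each running from zero to the number of missing outcomes in that arm. It also says that missing at random cannot be established for follow-up observations.

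On supporting analyses, section 4.5 says "a supporting analysis will be performed using the FAS Immunogenicity", and section 6.1 assigns supporting work to the FAS population. Sections 5.2 and 6.5.1.3 rule out imputation for these.

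**The concern.** The check is aimed at a population from which its own target has been filtered out. Being in the PPS requires paired valid serology, so a child who missed the Day 29/57 draw, or whose Day 1 sample was lost, cannot contribute a missing value. A baseline titer absent because the sample is missing cannot be imputed in this set, and the seroconversion grid cannot extend to the children whose samples are missing.

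At stake is the robustness statement, not the non-inferiority decision. A report that follows the SAP literally would state that the conclusions withstood a missing-data analysis when absent samples had never been varied. The SAP itself doubts missing at random for follow-up data, so this is the check a reader would look for.

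**Working it through.** **Tracing the sets**

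1. Sensitivity analysis population = PPS (SAP 6.5.1.3 and Appendix C agree).
2. PPS is contained in FAS Immunogenicity (SAP 4.5).
3. FAS Immunogenicity requires valid results at both visits (SAP 4.4).
4. So a child with no valid sample at either visit is outside the analysis population.
5. What can remain: SAP 4.4 does not say that results must be valid for every strain, and section 6.5.1.3 says "Each of the four strains will be analyzed separately". A child with both samples but one failed strain assay could stay in the PPS with that titer missing. No failure rate is given.

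**Inputs** (Protocol 8.5, SAP 2.3): 1450 QIVc and 725 QIV evaluable; B-strain seroconversion rate (SCR) 69% in both arms; SCR margin 10 points; GMT ratio margin 1.5; SD of natural-log titer 1.3; B-strain GMT ratio 0.84, which the synopsis labels QIVc/QIV, so 1/0.84 = 1.190 on the QIV/QIVc scale.

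**The plan's own figures first**

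- B-strain SCR power: SE = sqrt[0.69 × 0.31 × (1/725 + 1/1450)] = 0.0210; 0.10/0.0210 − 1.96 = 2.79; power 99.7% (stated 99.7%).
- B-strain GMT power: SE = 1.3 × sqrt(1/725 + 1/1450) = 0.0591; (0.4055 − 0.1744)/0.0591 − 1.96 = 1.95; power 97.43% (stated 97.42%).
- Recruitment: 725/0.9 rounds up to 806 and 1450/0.9 to 1612; total 2418 (stated 2418).

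**Tipping grid for SCR**

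Observed: 500/725 and 1000/1450 (69.0% each). If a fraction f is missing, the missing counts are n × f/(1 − f), rounded: at 10%, 1450 × 0.1/0.9 = 161 and 725 × 0.1/0.9 = 81. Each grid point adds a seroconverters among the missing QIVc children and b among the missing QIV children. The upper 95% limit δ for QIV minus QIVc is the Miettinen-Nurminen limit named in SAP 6.1. It solves (p1 − p2 − δ)/sqrt(V) = −1.96, where V = [q1(1 − q1)/n1 + q2(1 − q2)/n2] × (n1 + n2)/(n1 + n2 − 1) and q1, q2 are the maximum-likelihood rates restricted to q1 − q2 = δ. SAP 6.5.1.3 also mentions exact limits; those were not computed.

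The worst corner has every missing QIV child and no missing QIVc child seroconverting.

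| Assumed missing | QIVc / QIV missing | Grid points | Points above 10% | Worst-corner upper limit |
|---|---|---|---|---|
| none | 0 / 0 | 1 | 0 | 4.07% |
| 1% | 15 / 7 | 16 × 8 = 128 | 0 | 5.06% |
| 5% | 76 / 38 | 77 × 39 = 3,003 | 0 | 8.95% |
| 6% | 93 / 46 | 94 × 47 = 4,418 | 0 | 9.95% |
| 6.25% | 97 / 48 | 98 × 49 = 4,802 | 4 | 10.19% |
| 10% | 161 / 81 | 162 × 82 = 13,284 | 1,030 (7.8%) | 13.85% |

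At 10%, the worst corner is 581/806 − 1000/1611 = 10.0 points. If 56 of the 81 missing QIV children (69%) seroconvert, QIVc passes once 14 of its 161 (9%) do. If all 81 do, it needs 62 of 161 (39%).

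The 1% row illustrates what the present set might contain, namely strain-level failures only. The 5% to 10% rows illustrate a set that keeps children with missing samples.

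**GMT ratio, B strain**

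Complete-case upper limit = 1.190 × exp(1.96 × 0.0591) = 1.337. To reach 1.5, missing QIVc titers would have to be lower by a factor exp[(ln 1.5 − 1.96 × 0.0591 − ln 1.190)/f], which is 10.0 at f = 0.05 and 3.2 at f = 0.10. Extra imputation variance is ignored.

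**The case against.** **The analysis is exploratory and the stakes are low.** This stands. Section 6.5.1.3 only says that it may be done, and it is outside the success rule. At planned values no grid point fails at 6% missing or below, and failure at 10% needs very poor seroconversion among the missing QIVc children. The 10% case also treats the whole drop-out allowance as missing serology, which the documents do not say. None of this makes the stated set suitable for its stated purpose.

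**Something is left to impute.** A reader might infer that the PPS has no missing titers and the grid collapses to one point. The documents do not support that, because strain-level failures may remain. But those are not missing samples, and a small grid built on them would look reassuring without addressing absent children.

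**Other analyses may cover the gap.** A reader might take the FAS population in SAP 6.1 as a wider supporting set. That label sits awkwardly with sections 4.5 and 6.5.1.2, which name the FAS Immunogenicity. Under either reading the analysis is complete-case. The unadjusted GMT ratio in 6.5.1.3 needs no Day 1 titer but does not replace a missing post-vaccination one.

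**Missed draws as deviations.** Section 4.5.1 lists "Key study procedures missed or performed out of window" as a deviation category, so a reader might infer that every child without a sample is excluded twice. That is too strong. The same section says that early termination, and the later assessments missed because of it, are not deviations. The category can reach only a child who stays in the study and misses a draw.

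**A wider set could differ in other ways.** This stands as a caution on the remedy. Protocol 3.5 reserves about 3 mL of each CMI-group sample for antibody testing, and SAP 4.4 and 4.5 do not exclude that group. Removing it from the sensitivity set alone would mix two changes.

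**Conclusion.** The concern holds as a mismatch between the sensitivity analysis and its population. Followed literally, Appendix C cannot impute a missing or wholly invalid sample, and no other planned analysis imputes one. This rests on the set definitions and needs no assumed rate.

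The sizes do rest on assumptions: the missing rates, observed data equal to the planning values, and Miettinen-Nurminen limits. On that basis the B-strain SCR conclusion survives every possible assignment of missing outcomes up to 6% missing, and 7.8% of assignments overturn it at 10%. A reader might infer that the non-inferiority conclusion is itself in doubt. The documents and these figures do not support that: the conclusion looks fairly robust, and the primary result and success rule do not depend on this analysis. The loss is that the plan could not demonstrate the robustness it sets out to show. It should be corrected before unblinding.

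**What to change.** - In SAP 6.5.1.3 and Appendix C, replace the per-protocol set with randomised and vaccinated children who meet all other PPS criteria, dropping only the requirement for valid results at both visits.
- State that a missed draw by a child still in the study (section 4.5.1) does not exclude the child from this set. Early terminators are already covered there.
- Treat the CMI group exactly as the primary PPS does, so that any shift reflects missing titers alone.
- Reconcile the two statements of whether the analysis is optional (6.5.1.3) or definite (Appendix C).
- Optional: add a GMT imputation that lowers missing QIVc titers by a fixed amount. Drawing both arms' missing values from one arm, as Appendix C plans, pulls the ratio toward 1; for the B strains at 10% missing, 1.190^0.9 = 1.170.

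A separate matter, not part of this fix: SAP 6.3, SAP 4.4, SAP section 7 and Protocol 8.3.4 disagree on where the influenza and prohibited-medication exclusions apply and should be reconciled on their own.

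The cost is SAP text and minor programming, with no new data. The primary analysis, margins, alpha, sample size and success rule stay as they are.
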